- 1050 • Diabetes Locus of Control

1051 **7.4.3. AE Assessment**

1052 The participant will be asked about any of adverse events, adverse device effects, and device
1053 issues since the last visit. The participant will also be asked if there were any low BGs <54 mg/dL,
1054 high BGs >300 mg/dL, or ketones ≥ 3.0 mmol/L since the last visit.

1055 Once all training activities are completed, the participant will be given adequate supplies and
1056 study devices to last until the subsequent clinic visit. An appointment for Visit 5 will be scheduled.

1057 **7.5. Home Use of DiAs in Phase 2 Mode**

1058 The participant will complete a minimum of 8 weeks of DiAs use in Phase 2 Mode at home.

1059 During the course of Phase 2, participants will complete EMA surveys and post-phase
1060 questionnaires.

1061 **7.5.1. Phase 2 EMA Surveys**

1062 Over the course of 2-3 days every two weeks of Phase 2, the participant will be asked to complete
1063 a “Daily Diary” with 3-5 entries of 3-4 questions each day, for a minimum total of 48 entries per
1064 participant during each Phase.

1065 **7.5.2. Post-Phase 2 Questionnaires Week 7**

1066 All participants will be sent the following questionnaires on week 7 (day 42 of Phase 2) and will
1067 be asked to complete them within 1 week:

- 1068 • Technology Acceptance (burdens subscale only)

CLINICAL PROTOCOL

1069 • Pittsburgh Sleep Quality Index

1070 • T1-Diabetes Distress Scale

1071 **7.5.3. Post-Phase 2 Questionnaires Week 8**

1072 All participants will be sent the following questionnaires on week 8 (day 49 of Phase 2) and will
1073 be asked to complete them within 1 week:

1074 • Hypoglycemia Fear Survey

1075 • Hyperglycemia Avoidance Scale

1076 • Confidence in Diabetes Self-Care Scale

1077 **7.6. Visit 5 – Phase 3 Initiation**

1078 The participant will begin Phase 3 according to the randomization scheme either via web
1079 conference or an office visit. The participant will remotely receive a mode change for Phase 3.
1080 Study staff will review the features of the Phase 3 system and answer any questions.

1081 **7.6.1. Training on Phase 3 DiAs Mode**

1082 Participants randomized to de-escalation will have any questions answered about resuming use
1083 of the DiAs system in SAM.

1084 **7.6.2. Phase 3 Initiation Questionnaires**

1085 Participants randomized to de-escalation will complete the following questionnaires:

1086 • INSPIRE (revised for DSS)

1087 • Diabetes Locus of Control

1088 **7.6.3. Adverse Event Assessment**

1089 The participant will be asked about any of adverse events, adverse device effects, and device
1090 issues since the last visit. The participant will also be asked if there were any low BGs <54 mg/dL,
1091 high BGs >300 mg/dL, or ketones ≥ 3.0 mmol/L since the last visit.

1092 Once all training activities are completed, the participant will be given adequate supplies and
1093 study devices to last until the subsequent clinic visit. An appointment for Visit 6 will be scheduled.

1094 Participants will be encouraged to contact the study team between visits as needed (i.e. report
1095 adverse events in real-time).

1096 **7.7. Home Use of DiAs in Phase 3 Mode**

1097 The participant will complete a minimum of 8 weeks of Phase 3 at home. During the course of
1098 Phase 3, participants will complete EMA surveys and post-phase questionnaires.

CLINICAL PROTOCOL

1099 **7.7.1. Phase 3 EMA Surveys**

1100 Over the course of 2-3 days every two weeks of Phase 3, the participant will be asked to complete
1101 a “Daily Diary” with 3-5 entries of 3-4 questions each day, for a minimum total of 48 entries per
1102 participant during each Phase.

1103 **7.7.2. Post-Phase 3 Questionnaires Week 7**

1104 Participants randomized to de-escalation will be sent the following questionnaires on week 7
1105 (day 42 of Phase 1) and will be asked to complete them within 1 week:

- 1106 • Pittsburgh Sleep Quality Index
- 1107 • T1-Diabetes Distress Scale

1108 **7.7.3. Post-Phase 3 Questionnaires Week 8**

1109 Participants randomized to de-escalation will be sent the following questionnaires on week 8
1110 (day 49 of Phase 1) and will be asked to complete them within 1 week:

- 1111 • Hypoglycemia Fear Survey
- 1112 • Hyperglycemia Avoidance Scale (HAS)
- 1113 • Confidence in Diabetes Self-Care Scale

1114 **7.8. Visit 6 - Study Exit**

1115 Participants will participate in a Study Exit visit either via web conference or an office visit.
1116 Participants will return to their standard diabetes care using their personal equipment. The study
1117 team will be available to answer questions about insulin parameters.

1118 The participant will be asked to return all investigational study devices (e.g. study insulin pump,
1119 study, CGM, study phone, other associated supplies) either via mail or at an office visit.
1120 Participants may keep the study glucometer and ketone meter.

1121 **7.8.1. Study Exit Questionnaires**

1122 Participants randomized to de-escalation will complete the following questionnaires:

- 1123 • ABACUS

1124 **7.8.2. Adverse Event Assessment**

1125 The participant will be asked about any of adverse events, adverse device effects, and device
1126 issues since the last visit. The participant will also be asked if there were any low BGs <54 mg/dL,
1127 high BGs >300 mg/dL, or ketones ≥ 3.0 mmol/L since the last visit.

CLINICAL PROTOCOL

1128 **7.9. Post Study Check-In Visit (Visit 7)**

1129 Approximately 48 hours after the home use of the equipment, the study team will contact the
1130 participant via phone/email/text to assess:

- 1131 • Adverse events, adverse device effects, and device issues
1132 • Blood glucose values <60 mg/dL and >300 mg/dL

1133 **Chapter 8 Testing Procedures**

1134 **8.1. Laboratory / Point of Care Testing**

1135 **8.1.1. HbA1c**

- 1136 • A blood sample will be obtained at screening to obtain a baseline hemoglobin A1c level.
- 1137 • HbA1c level may be measured by study team using the DCA2000, a comparable point of
1138 care device, at time of screening
- 1139 • Labs may be obtained at a local laboratory (e.g. LabCorp) convenient to the participant.
- 1140 • Blood test may be obtained within 14 days prior to enrollment may be used for eligibility
1141 purposes.
- 1142 • Sample collected at randomization and end of study will be used for statistical purposes.

1143 **8.1.2. Comprehensive Metabolic Panel**

- 1144 • A blood sample will be obtained at screening to assess kidney and liver functioning.
- 1145 • Labs may be obtained at a local laboratory (e.g. LabCorp) convenient to the participant.
- 1146 • Blood test may be obtained within 14 days prior to enrollment may be used for eligibility
1147 purposes.

1148 **8.1.3. Thyroid Stimulating Hormone**

- 1149 • A blood sample will be obtained at screening to assess thyroid function.
- 1150 • Labs may be obtained at a local laboratory (e.g. LabCorp) convenient to the participant.
- 1151 • Blood test may be obtained within 14 days prior to enrollment may be used for eligibility
1152 purposes.

1153 **8.1.4. Pregnancy Test**

1154 A blood/urine pregnancy test will be required for women of childbearing potential at the
1155 screening visit, and between each phase . Tests must be negative to participate in the study.

1156 **Chapter 9 Questionnaires & Ecological Momentary Analysis**

1157 **9.1. Diabetes Specific Personality Questionnaire**

1158 The Diabetes Specific Personality Questionnaire is based on the original Six Factor Personality
1159 Questionnaire [81], a well-validated measure that was adapted for the diabetes-specific version
1160 of the questionnaire. The Six Factor Personality Questionnaire is a measure of six personality
1161 dimensions each consisting of three facet scales, measured by 108 Likert items. The Six Factor
1162 Personality Questionnaire facet scales are organized in terms of six factor scales. The Diabetes
1163 Specific Personality Questionnaire assesses three personality factors – conscientiousness,
1164 obsessive-compulsiveness, and openness. In this study, the Diabetes Specific Personality
1165 Questionnaire is used to explore whether personality type is associated with willingness and/or
1166 ability to effectively engage with the DSS. Administration time is approximately 15 minutes.

1167 **9.2. ABACUS**

1168 This is a structured interview used to provide a very brief assessment of carbohydrate counting
1169 and diabetes self-management skills important to effective engagement consisting of a series of
1170 25 questions assessing health literacy and health numeracy in people with T1DM [84].. The
1171 interviewer evaluates the subject answer to each question on a scale ranging from 1 (No
1172 competency) to 3 (Full competency); the sum yields to a total score. The higher the score, the
1173 higher the levels of health literacy and numeracy of the subject. Administration time is
1174 approximately 10-20 minutes.

1175 **9.3. Diabetes Locus of Control**

1176 This questionnaire [85] was developed for use on adults (18-80 y.o.) The scale consists of 18 items
1177 measuring the individual’s personal beliefs about their control over their diabetes management
1178 and outcome: 6 items measuring internal locus of control, 6 items measuring powerful others
1179 locus of control, and 6 items measuring chance locus of control. A 6-point Likert-type scale is used
1180 in which 0 indicates ‘strongly disagree with the statement’ and 5 indicates ‘strongly agree with
1181 the statement.’ Administration time is approximately 5 minutes.

1182 **9.4. Confidence in Diabetes Self-Care Scale**

1183 This is a short 20-item self-report questionnaire assessing self-efficacy, the perceived ability to
1184 perform diabetes self-care tasks, in patients with T1DM [87]. Items are constructed to cover all
1185 domains of self-care as well as social skills. Each item is preceded by, “I believe I can...” with the
1186 strength of this belief rated on a 5-point Likert scale ranging from 1 (“No, I am sure I cannot”) to
1187 5 (“Yes, I am sure I can”). Administration time is approximately 10 minutes.

CLINICAL PROTOCOL

1188 **9.5. Clarke's Hypoglycemia Awareness Scale**

1189 The scale comprises eight questions characterizing the participant's level of hypoglycemia
1190 awareness, as well as risk for exposure to episodes of moderate and severe hypoglycemia [88].
1191 It also examines the glycemic threshold for symptomatic responses to hypoglycemia. A score of
1192 four or more on a scale of 0 to 7 implies impaired awareness of hypoglycemia. Administration
1193 time is approximately 5 minutes.

1194 **9.6. The Diabetes Distress Scale**

1195 This is a measure that reflects diabetes-specific quality of life and emotional well-being [90]. The
1196 Diabetes Distress Scale is a measure of diabetes-related distress over a number of domains (e.g.
1197 diabetes management regimen, interpersonal distress) and consists of a scale of 17 items. These
1198 include items from each of four domains central to diabetes-related emotional distress. Patients
1199 rate the degree to which each item is currently problematic for them on a 6-point Likert scale,
1200 from 1 (no problem) to 6 (serious problem). Administration time is approximately 5 minutes.

1201 **9.7. Hypoglycemia Fear Survey**

1202 This questionnaire will be used to determine if the PF and DSS is associated with reduced fear of
1203 hypoglycemia. The Hypoglycemia Fear Survey-II [91] was developed to measure behaviors and
1204 worries related to fear of hypoglycemia in adults with T1DM. It is composed of 2 subscales, the
1205 Behavior and Worry. Behavior items describe behaviors in which patients may engage to avoid
1206 hypoglycemic episodes and/or their negative consequences (e.g., keeping blood glucose levels
1207 higher, making sure other people are around, and limiting exercise or physical activity). Worry
1208 items describe specific concerns that patients may have about their hypoglycemic episodes (e.g.,
1209 being alone, episodes occurring during sleep, or having an accident). Items are rated on a 5-point
1210 Likert scale (0=never, 4=always), with higher scores indicating higher fear of hypoglycemia.
1211 Administration time is approximately 10 minutes.

1212 **9.8. Hyperglycemia Avoidance Scale**

1213 This measure is used to assess the extent of potentially problematic avoidant attitudes and
1214 behaviors in people with T1DM [91]. The Hypoglycemia Avoidance Scale reliably quantifies
1215 affective and behavioral aspects of hyperglycemia avoidance and is used to assess the extent of
1216 potentially problematic avoidant attitudes and behaviors regarding hyperglycemia in people with
1217 T1DM. It has 24 items plus two additional optional items asking about the highest level of daily
1218 blood glucose or HbA1c measures the individual would feel comfortable having. Administration
1219 time is approximately 10 minutes.

CLINICAL PROTOCOL

1220 **9.9. Pittsburgh Sleep Quality Index**

1221 This questionnaire will be used to assess whether the PF and DSS improve sleep quality and
1222 quantity. The Pittsburgh Sleep Quality Index [93] is a self-report questionnaire that assesses sleep
1223 quality over a 1-month time interval. The measure consists of 19 individual items, creating 7
1224 components that produce one global score: the higher the global score, the poorer the sleep
1225 quality. Administration time is approximately 5-10 minutes.

1226 **9.10. Technology Acceptance and Expectations Survey (burdens subscale only)**

1227 The Technology Acceptance Surveys [94-95] were developed for an artificial pancreas camp study
1228 in adolescents. The 38 items in the questionnaire were based on interviews conducted with
1229 individuals who had participated in previous artificial pancreas trials about their experience
1230 regarding the device. It was subsequently adapted to assess these same measures for the PF and
1231 DSS. It assesses both positive and negative experiences with PF and DSS, including blood glucose
1232 management, device burden, and overall satisfaction. Items are rated on a 5-point scale. In this
1233 study only the burden subscale will be used. The Technology Expectations Survey has the same
1234 items included on the Technology Acceptance Survey but asks whether the individual expects to
1235 experience the various benefits and burdens from use of a device. Administration time is
1236 approximately 10 minutes.

1237 **9.11. INSPIRE (revised for DSS)**

1238 This questionnaire will be used to assess patient preferences to support effective onboarding and
1239 successful continued use of the PF and DSS. The INSPIRE survey was developed to assess various
1240 aspects of a user's experience regarding automated insulin delivery for both patients and family
1241 members. The surveys include various topics important to patients with T1DM and their family
1242 members based upon >200 hours of qualitative interviews and focus groups. It was adapted by
1243 its developer for use with the PF and DSS. The survey includes 22 items. Response options include
1244 a 5-point Likert scale from strongly agree to strongly disagree, along with an N/A option.
1245 Administration time is approximately 5 minutes.

1246 **9.12. Ecological Momentary Analysis (EMA)**

1247 In addition to the behavioral data automatically recorded (e.g. insulin dosing, interactions with
1248 system), an EMA procedure will be used to track the users' daily experiences of trust in the
1249 system, emotional well-being, treatment satisfaction, and diabetes-related concerns and burden.
1250 Using a brief daily survey, we will capture the dynamic changes in participant experience
1251 throughout the day and the associations between users' subjective experience and their
1252 reactions to/interactions with the PF and DSS devices. This will be the first use of EMA with
1253 decision support systems.

CLINICAL PROTOCOL

1254 During each treatment condition, over the course of 2-3 days every two weeks, the participant
1255 will be asked to complete a “Daily Diary” with 3-5 entries of 3-4 questions each day, for a
1256 minimum total of 48 entries per participant during each Phase.

1257 The DiAs phone will display a text message containing a link to the survey. Surveys will be
1258 triggered at fixed times, including a morning survey ~1h after waking up and an end-of-the-day
1259 survey around 8-9 PM. Participants will be able to delay (up to 30 min) or skip (up to 2 per day
1260 excluding at wake up) surveys for their convenience.

1261 Participants will respond to questions on a 5-point Likert scale (0=Not at All, 4=Extremely). The
1262 first Diary for each day will contain two additional items for rating sleep quantity/quality.

1263 The Daily Diary questions are shown below and are intended to assess agreement, trust,
1264 treatment satisfaction, diabetes burden, self-efficacy, mood valence, energy level, and physical
1265 well-being.

1266 • Quality of Life Parameters

1267 ▪ At this moment, to what extent do you feel...

1268 ➤ Burdened by your diabetes treatment?

1269 ➤ Worried about your blood sugar levels?

1270 ➤ In a positive or good mood?

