CLINICAL PROTOCOL

409 **Aim 1.1** the superiority of the PF over Sensor-augmented mode (SAM) in controlling GV. PF is a
410 system designed to provide patients with *actionable information* about glucose control in general
411 and GV in particular (e.g. estimated HbA1c (eA1c), risk of hypoglycemia, and activity level);

412 **Aim 1.2** the superiority of the DSS over SAM in controlling GV. DSS is a CGM-based system that
413 includes PF and further assists with treatment recommendations for common metabolic
414 challenges;

415 **Aim 1.3** the overall non-inferiority of DSS over PF intervention to control GV and superiority of
416 DSS to maintain tight glycemic control over time (lower variations of GV in time).

417 **Aim 2 (personalization of treatment policy)** We hypothesize that the participants in this study
418 will have technology intervention preferences (e.g. PF or DSS) that can be predicted by key
419 psychosocial and behavioral parameters and are prognostic of the level of GV control achievable
420 by the intervention. We will:

421 **Aim 2.1** confirm that technology acceptance and trust are predictive of the level of GV control
422 achieved during the study (see Aim 1), regardless of the type of DSS system in use. We
423 hypothesize that technology acceptance will correlate negatively with GV: i.e. higher technology
424 acceptance leads to lower GV;

425 **Aim 2.2** explore the impact of technology expectations and experience on the performance of
426 each type of technology intervention (SAM, PF, DSS). For example, higher expectation will
427 negatively correlate with GV for the SAM treatment, but not the DSS treatment.

428 **Aim 2.3** assess the correlation between relevant psycho-behavioral traits with the performance
429 of PF vs DSS, identifying potential pathways to the corresponding optimal technology-based
430 treatment policies.

431 **1.3. Outcomes**

432 **1.3.1. Glycemic outcomes**

433 The primary outcome of this study will be Glucose Variability (GV) as measured by CGM-based
434 Coefficient of Variation (CV), as recommended by the International Consensus on Use of
435 Continuous Glucose Monitoring. To further characterize glucose control, we will compute other
436 CGM Consensus outcomes as well:

437 Average

438 Percent in different ranges:

439 ○ <50 mg/dL

440 ○ <54 mg/dL

[figure not shown]
CLINICAL PROTOCOL

- 441 ○ <60 mg/dL
- 442 ○ <70 mg/dL
- 443 ○ ≤70-≤180 mg/dL
- 444 ○ >180 mg/dL
- 445 ○ >250 mg/dL
- 446 ○ >300 mg/dL

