- 447

448 Each modality of treatment will be assessed using the last 4 weeks of CGM recordings, as we
449 expect most of the GV benefits of each intervention to be realized within the first 4 weeks of the
450 intervention, and a minimum of 24 days of data is considered optimal for CGM-based CV
451 determination.

452 1.3.2. Glucose Variability Reduction Achieved with CGM-based expert systems

453 General linear models (GLM) (repeated measures ANOVA) will be used to assess the significance
454 of the differences in average response between SAM, PF, and DSS across appropriate CGM-based
455 metrics. The particular design of the clinical study allow for Aims 1.1, 1.2, and 1.3 to each be
456 addressed independently in a randomized crossover analysis, as shown in Figure 4. While the
457 randomized order of the interventions (escalation vs de-escalation) allows for an objective
458 assessment of the average efficacy of each of them, we will introduce the order as a fixed factor
459 to verify if significant study effects can be detected. Finally, we will study the evolution of GV
460 within each modality period: GV and other CGM-based outcomes will be computed bi-weekly
461 (the minimum length of time for precise GV assessment) and entered in a repeated measures
462 GLM analysis; within-subject contrast (linear and polynomial) using 5 repeated measures per
463 condition to explore the evolution of the glycemic outcomes in time; Aim 1.3.

464
465

Figure 4: Multiple analyses enabled by study design to address Aim 1.1, 1.2 and 1.3

CLINICAL PROTOCOL

466 **1.3.3. Exploration of the effect of treatment escalation vs. de-escalation**

467 A key advantage of the proposed study design (beyond the optimal statistical power) is the
468 possibility to explore the glucose control and psycho-behavioral impact of features being added
469 and/or enhanced with prescriptive components (DSS), vs. features being limited to information
470 (PF) or even removed (SAM). We will perform this analysis by looking at the between factors in
471 the repeated ANOVA analysis, contrasting the escalation group vs. de-escalation group. While
472 not powered, this analysis will provide key insights in the future feature adaptation schemes
473 based on the ATI.

474 **1.3.4. Psychological and Behavioral Questionnaires**

475 As part of Aim 2, we will conduct robust psychosocial analyses of factors important to participant

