1653 Sample size determination is based on our related pilot studies of DSS. We estimate that the
1654 effect size of DSS vs. SAM will be $f^2=0.22$. Power calculations (G*Power 3.1.9.2) assuming $\alpha=0.017$
1655 (corrected for multiple comparisons), 95% power, correlation of 0.55 between the repeated
1656 measures, and attrition of 20%, yield a sample size of N=100 subjects to be randomized at
1657 baseline, with N=80 subjects completing the study. PF vs. SAM assumes the same effect size. We
1658 expect that while overall DSS effect vs. PF will be smaller than vs. SAM, GV control over time will
1659 be more consistent. Aim 1.3 analysis therefore assumes a small effect size (0.15) but 5 repeated
1660 measures (bi-weekly) in each condition with higher correlation (0.65), leading to an achieved
1661 power of 97.2% for this Aim.

1662 **14.2.2. Exploration of the effect of treatment escalation vs. de-escalation:**

1663 A key advantage of the proposed study design (beyond the optimal statistical power) is the
1664 possibility to explore the glucose control and psycho-behavioral impact of features being added
1665 and/or enhanced with prescriptive components (DSS), vs. features being limited to information
1666 (PF) or even removed (SAM). We will perform this analysis by looking at the between factors in
1667 the repeated ANOVA analysis, contrasting the escalation group vs. de-escalation group. While

CLINICAL PROTOCOL

1668 not powered, this analysis will provide key insights in the future feature adaptation schemes
1669 based on the ATI.

1670 **14.3. Outcome Measures**

1671 **14.3.1. Glycemic outcomes:**

1672 The primary outcome of this study will be Glucose Variability (GV) as measured by CGM-based
1673 Coefficient of Variation (CV), as recommended by the International Consensus on Use of
1674 Continuous Glucose Monitoring. To further characterize glucose control, we will compute other
1675 CGM Consensus outcomes as well:

- 1676 • Average
- 1677 • Percent in different ranges:
 - 1678 ○ <50 mg/dL
 - 1679 ○ <54 mg/dL
 - 1680 ○ <60 mg/dL
 - 1681 ○ <70 mg/dL
 - 1682 ○ ≤70-≤180 mg/dL
 - 1683 ○ >180 mg/dL
 - 1684 ○ >250 mg/dL
 - 1685 ○ >300 mg/dL
- 1686 • SD and coefficient of variation
- 1687 • LBGI, HBGI, ADRR

1688 Each modality of treatment will be assessed using the last 4 weeks of CGM recordings, as we
1689 expect most of the GV benefits of each intervention to be realized within the first 4 weeks of the

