1690 intervention, and a minimum of 24 days of data is considered optimal for CGM-based CV
1691 determination.

1692 **14.3.2. Glucose Variability Reduction Achieved with CGM-based expert systems:**

1693 General linear models (GLM) (repeated measures ANOVA) will be used to assess the significance
1694 of the differences in average response between SAM, PF, and DSS across appropriate CGM-based
1695 metrics. The particular design of the clinical study allow for Aims 1.1, 1.2, and 1.3 to each be
1696 addressed independently in a randomized crossover analysis, as shown in Figure 4. While the
1697 randomized order of the interventions (escalation vs de-escalation) allows for an objective
1698 assessment of the average efficacy of each of them, we will introduce the order as a fixed factor
1699 to verify if significant study effects can be detected. Finally, we will study the evolution of GV
1700 within each modality period: GV and other CGM-based outcomes will be computed bi-weekly
1701 (the minimum length of time for precise GV assessment) and entered in a repeated measures

CLINICAL PROTOCOL

1702 GLM analysis; within-subject contrast (linear and polynomial) using 5 repeated measures per
1703 condition to explore the evolution of the glycemic outcomes in time; Aim 1.3.

1704 **14.4. Exploration of the effect of treatment escalation vs. de-escalation**

1705 A key advantage of the proposed study design (beyond the optimal statistical power) is the
1706 possibility to explore the glucose control and psycho-behavioral impact of features being added
1707 and/or enhanced with prescriptive components (DSS), vs. features being limited to information
1708 (PF) or even removed (SAM). We will perform this analysis by looking at the between factors in
1709 the repeated ANOVA analysis, contrasting the escalation group vs. de-escalation group. While
1710 not powered, this analysis will provide key insights in the future feature adaptation schemes
1711 based on the ATI.

1712 **14.5. Psychological and Behavioral Questionnaires**

1713 *Quantitative* data on usability and satisfaction will be analyzed using simple descriptive statistics.
1714 In addition, we will analyze scores from the measures in the psychosocial assessment battery to
1715 determine if changes occur over time and between groups. Using SPSS 26, we will construct
1716 predictive models in the general linear modeling (GLM) framework to examine each set of

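### Aim 1.3 claims non-inferiority of DSS to PF on CV, but the plan has no margin or confidence-limit rule, and its 97.2% is not power for that claim

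*Combined protocol and SAP*

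**What the plan says.** Section 1.2 lists under Aim 1.3 "the overall non-inferiority of DSS over PF intervention to control GV and superiority of" "DSS to maintain tight glycemic control over time (lower variations of GV in time". The Aim therefore has two parts: non-inferiority on glucose variability, whose primary measure is the CGM coefficient of variation (CV), and superiority in stability over time.

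Sections 1.3.2 and 14.3.2 give the analysis: "General linear models (GLM) (repeated measures ANOVA) will be used to assess the significance" "of the differences in average response between SAM, PF, and DSS across appropriate CGM-based" metrics. They add linear and polynomial within-subject contrasts on bi-weekly values to explore the time course, and label this Aim 1.3. The word non-inferiority does not recur in the supplied text, which states no margin, confidence-limit rule or one-sided alpha.

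On power, section 14.2.1 says the authors "expect that while overall DSS effect vs. PF will be smaller than vs. SAM, GV control over time will" "be more consistent. Aim 1.3 analysis therefore assumes a small effect size (0.15) but 5 repeated" "measures (bi-weekly) in each condition with higher correlation (0.65), leading to an achieved" "power of 97.2% for this Aim".

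**The concern.** A difference test and a non-inferiority test answer different questions. A significant result favouring DSS would imply non-inferiority. A non-significant result cannot, because it is also what a modest real deficit tends to produce. Without a margin, the plan cannot reach the conclusion it names when DSS and PF perform about equally, which is the case a non-inferiority claim is meant to cover.

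At stake is a named claim on the primary outcome. A non-significant comparison could be reported as non-inferiority, and a margin chosen after the data are seen would not be credible. The 97.2% adds to the risk because a reader may take it to cover both parts of the Aim.

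**Working it through.** **1. The plan's own figure.** Inputs from section 14.2.1: f = 0.15, m = 5 measures, correlation 0.65, alpha 0.017, N = 80. For a repeated-measures F test, lambda = f² × N × m / (1 − rho) = 0.0225 × 80 × 5 / 0.35 = 25.7, with 4 and 316 df. Power is 0.9721, so the 97.2% reproduces. A two-group by time interaction gives the same value. No margin enters the calculation.

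An 8-week period holds four 2-week windows. With m = 4, lambda = 20.6 and power is 0.941.

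**2. The one valid route: DSS significantly better than PF.** This uses two-sided alpha 0.017 and 80 completers.
- True difference zero: 0.017 / 2 = 0.85% of trials.
- The plan's 0.15 read as a two-condition f, that is, a difference of 2 × 0.15 = 0.30 SD: lambda = 0.0225 × 80 × 2 / (1 − rho), which is 8.0 at rho 0.55 and 10.3 at rho 0.65. Power is 65.2% and 77.7%.

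**3. How often a real DSS deficit is non-significant.** The plan gives no SD for 4-week CV and none for PF. As an assumption, take the pilot SDs in section 1.1.2 (0.08 control, 0.06 DSS, 48-hour periods) and rho 0.55-0.65. The paired SD is √(s1² + s2² − 2·rho·s1·s2).
- Low end: SDs 0.06 and 0.06, rho 0.65: √0.00252 = 0.050, standard error 0.050/√80 = 0.0056.
- High end: SDs 0.08 and 0.06, rho 0.55: √0.00472 = 0.069, standard error 0.0077.

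The high end agrees with the pilot. If its p = 0.045 with 24 participants came from a paired t test, then t = 2.12 and the paired SD is 0.03 × √24 / 2.12 = 0.069.

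The table uses the noncentral t with 79 df and critical value 2.438. One CV point is 0.01.

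| True DSS deficit | Non-significant, paired SD 0.050 | Non-significant, paired SD 0.069 |
|---|---|---|
| 1.0 point | 74% | 87% |
| 1.5 points | 41% | 68% |
| 2.0 points | 13% | 43% |
| 3.0 points | 0.2% | 7.4% |

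The 4-week SD may be smaller. With SD 0.05 in both conditions and rho 0.55-0.65, the first three rows become 61-70%, 22-35% and 3.5-9.4%.

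**4. What a non-inferiority test would deliver.** This is an illustration at true difference 0, one-sided alpha 0.0085 and paired SD 0.050-0.069. Power is 57-87% for a 2.0-point margin and 32-59% for 1.5 points. With SD 0.05 in both conditions it is 91-97% and 65-78%.

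**The case against.** The strongest reply is that the significant-benefit route may be quite likely. Section 14.2.1 expects DSS to differ less from PF than from SAM, but less is not zero. If the 0.15 is the DSS-PF effect, that route succeeds in about two thirds to three quarters of trials. This stands, so a reader should not infer that the plan has almost no way to reach its conclusion. That holds only if DSS and PF are truly about equal. The reply is conditional in turn, because the 0.15 may belong only to the over-time test.

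A second reply is that the 97.2% was never meant for non-inferiority: the sentence derives it from the expectation of steadier control over time. This also stands. A reader might infer that the figure is wrong, but the arithmetic is right and the fault lies in the label.

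Third, nothing in the documents says that a non-significant result will be reported as non-inferiority. That is correct, and no such intention should be attributed to the sponsor. The gap remains, because the text gives no other rule.

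Finally, Figure 4, cited for how the three sub-aims are addressed, is not available here. A margin given only in a figure would be unusual, but this cannot be excluded.

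**Conclusion.** The point holds as a mismatch between claim, analysis and stated power. Aim 1.3 names non-inferiority, the written analysis can support it only through a significant DSS benefit, and no power is stated for it.

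The exposure concerns small deficits: about 1 to 2 CV points, against a pilot DSS effect of 3 points (0.36 to 0.33). A 3-point deficit would be missed in under 8% of trials, so the stronger inference that a large disadvantage could pass unnoticed is not supported. Nor does the point touch Aims 1.1 and 1.2 or N=100, which rest on the separate DSS-SAM and PF-SAM calculation.

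The miss rates depend on pilot SDs from 48-hour periods and would fall if 4-week SDs are smaller. The absence of a margin and what the 97.2% measures do not depend on any SD.

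**What to change.** 1. In section 14.3.2, conclude non-inferiority only if the upper confidence limit for mean CV(DSS) minus CV(PF) lies below a margin fixed and justified before analysis. State the per-tail alpha; 0.0085 would match the two-sided 0.017. Alternatively, reword that part of Aim 1.3 as estimating the DSS-PF difference with its confidence interval.
2. In section 14.2.1, name the over-time test to which the 97.2% belongs and restate it for the number of bi-weekly windows actually available (94.1% with four). If the non-inferiority claim is kept, give its power separately.

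The cost is wording and one recalculated power figure, with no new data or participants. There are two downsides. The stated power for Aim 1.3 will look less favourable. Also, a confidence limit does not cure a feature of the design: PF is Phase 2 in both sequences (sections 6.4 and 7.4), so a non-linear period effect stays mixed with the DSS-PF difference.
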